4.0 STUDY POPULATION

4.1 Inclusion Criteria

In order to participate in this study, a patient must meet all of the criteria listed in this section:

- 1. Newly diagnosed histologically or cytologically gastric adenocarcinoma. (Siewert III acceptable: the bulk of tumor should be in stomach; gastric tumors with extension to the gastroesophageal junction are permitted.) Patients with T1-3N0-2 are eligible. Patients with N3, or T4 disease are not eligible.
- 2. Known T-stage defined by EUS. Must have had CT of the chest/abdomen/pelvis with IV contrast.
- 3. Medically eligible to receive SOC chemotherapy.

- 4. At least 19 years of age.
- 5. ECOG performance status ≤ 2 (see Appendix A)
- 6. Normal bone marrow and organ function as defined below:
 - a. Absolute neutrophil count $\geq 1,500$ cells/mm³
 - b. Platelets $\geq 100,000 \text{ cells/mm}^3$
 - c. Creatinine clearance > 50 mL/min
- 7. The effects of the various chemotherapy agents used in this study on the developing human fetus are unknown. For this reason, women of childbearing potential and men must agree to use adequate contraception (hormonal or barrier method of birth control, abstinence) prior to study entry and for the duration of study participation. Should a woman become pregnant or suspect she is pregnant while participating in this study, she must inform her treating physician immediately. Men treated or enrolled on this protocol must also agree to use adequate contraception prior to the study, for the duration of the study, and one month after completion of the study
- 8. Ability to understand and willingness to sign an IRB approved written informed consent document (or that of legally authorized representative, if applicable).

4.2 Exclusion Criteria

In order to participate in this study, a patient must not meet any of the criteria listed in this section:

- 1. Prior surgery, radiation, or chemotherapy for gastric or esophageal cancer.
- 2. Prior surgery to the esophagus or stomach that would alter the radiation treatment field or stomach motion.
- 3. Siewert I-II GE junction tumor.
- 4. Any active malignancy within 2 years of enrollment that may alter the course of gastric cancer. (Apparently cured localized malignancy or advanced, but indolent malignancy with significantly more favorable prognosis are allowed).
- 5. Currently receiving any other investigational agents.
- 6. A history of allergic reactions attributed to compounds of similar chemical or biologic composition to chemotherapeutic agents used in the study.
- 7. Uncontrolled intercurrent illness including, but not limited to, ongoing or active infection, diabetes, symptomatic congestive heart failure, unstable angina pectoris, or cardiac arrhythmia that are considered clinically significant as determined by the treating physician.

- 8. Pregnant and/or breastfeeding. Women of childbearing potential must have a negative pregnancy test within 14 days of study entry.
- 9. Patients with HIV are eligible unless their CD4+ T-cell counts are < 350 cells/mcL or they have a history of AIDS-defining opportunistic infection within the 12 months prior to registration. Concurrent treatment with effective ART according to DHHS treatment guidelines is recommended. Recommend exclusion of specific ART agents based on predicted drug-drug interactions (i.e. for sensitive CYP3A4 substrates, concurrent strong CYP3A4 inhibitors (ritonavir and cobicistat) or inducers (efavirenz) should be contraindicated).

4.3 Inclusion of Women and Minorities

Both men and women and members of all races and ethnic groups are eligible for this trial.

5.0 **REGISTRATION AND ENROLLMENT PROCEDURES**

The following steps must be taken before enrolling patients on this study:

- 1. Registration of consented patient in the Siteman Cancer Center OnCore database
- 2. Assignment of unique patient number (UPN)
- 3. Confirmation of patient eligibility by Washington University School of Medicine (WUSM)

Patients must not start any protocol intervention or procedures prior to signing of informed consent. All consented patients at all sites must be registered in the Siteman Cancer Center OnCore database at WUSM.

5.1 **Registration in OnCore Database**

Patient registration to the Siteman Cancer Center OnCore database must occur within one business day of the patient signing consent.

The following patient registration information must be scanned and emailed to the WUSM research coordinator on the day the patient signs consent:

- 1. Complete and submit manual registration form:
 - a. Your name and contact information (telephone number, fax number, and email address)
 - b. Your site PI's name, the registering MD's name, and your institution name
 - c. Patient's race, ethnicity, sex, ZIP code, country, and DOB
 - d. Three letters (or two letters and a dash) for the patient's initials
- 2. Currently approved protocol version date
- 3. Copy of signed consent form (patient name may be blacked out)
- 4. Planned date of enrollment

5.2 Assignment of UPN

Each patient will be identified with a unique patient number (UPN) for this study that will include a 3-digit site number (contact the study team for the site number) and a 2-digit sequential number beginning with 01 for the first patient. The UPN must not include patient initials or other identifying information. All data will be recorded with this identification number on the appropriate CRFs.

5.3 Confirmation of Patient Eligibility and Enrollment

Patient eligibility will be confirmed using the information listed below and scanning and emailing it to the WUSM research coordinator at least two business days prior to enrolling the patient:

- 1. Completed eligibility checklist, signed and dated by a member of the study team
- 2. Copy of appropriate source documentation confirming patient eligibility

Once the patient has been confirmed to be eligible for enrollment, the WUSM coordinator will forward verification of enrollment and the UPN via email.

5.4 Patient Enrollment Submissions

Patient enrollment packets may be submitted Monday through Friday between 8am and 5pm CT. Exceptions will be evaluated and approved on a case-by-case basis. Patient eligibility and subsequent enrollment will be confirmed by the WUSM research coordinator or designee by email within one business day of submission. Verification of eligibility and registration must be kept in the patient chart.

5.5 Screen Failures

Screen failures are defined as participants who consent to participate in the clinical trial but are not subsequently entered in the study. A minimal set of screen failure information is required to ensure transparent reporting of screen failure participants, to meet the Consolidated Standards of Reporting Trials (CONSORT) publishing requirements and to respond to queries from regulatory authorities. Minimal information includes demography, screen failure details, eligibility criteria, and any serious adverse event (if applicable).

5.6 Strategies for Recruitment and Retention

This trial will be open to all patients irrespective of gender, race, or socioeconomic status. Patients will be identified in both the inpatient (consults) and outpatient setting.

6.0 TREATMENT PLAN

Consenting and eligible patients will receive adaptive SCRT (25 Gy in 5 fractions), followed by standard of care total neoadjuvant chemotherapy followed by standard of care gastrectomy or esophagogastrectomy. The recommended SOC chemotherapy options are CAPOX, FOLFOX, or FLOT, but any SOC total neoadjuvant chemotherapy may be given at the discretion of the treating medical oncologist after consultation with the study chair. Patients who are not able to complete their full total neoadjuvant therapy regimen prior to surgery may complete chemotherapy postoperatively at the discretion of the treating physician.

6.1 Safety Cohort and Early Stopping Rules

There will be a lead-in safety cohort of 5 patients, monitored for 30 days after completion of RT. If there is one treatment-related patient death, then the safety cohort will be expanded to 10 patients. If there are two or more treatment-related deaths, the radiation dose will be decreased to 20 Gy in 5 fractions. The trial will be terminated if there are more than three treatment-related deaths (equaling approximately 10% of the entire projected accrual).

Treatment-related grade 5 toxicities should be reported to the institutional PI within 24 hours and to the WUSM PI according to the timelines in Section 8.2.

For the purposes of the early stopping rules, "treatment-related" refers to both adaptive SCRT and SOC total neoadjuvant chemotherapy.

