2.3 Study Design

2.3.1 Overall Design

The hypothesis of this study is that adaptive SCRT followed by multiagent chemotherapy will result in a pCR of at least 20%.

Thirty-six patients with gastric adenocarcinoma will be enrolled in this study. There will be a lead-in cohort of 5-10 patients (see Safety Cohort and Early Stopping Rules) to ensure there are no grade 5 toxicities related to adaptive SCRT (or SOC chemotherapy after adaptive SCRT). All patients will receive radiation delivered with MR or CBCT guidance followed by sequential chemotherapy. Gastrectomy will occur 2-4 weeks after the completion of chemotherapy. Pathologic response, plan dosimetry, and oncologic outcomes will be evaluated. FDG PET/CTs are strongly encouraged at baseline but optional. Patients will be followed on study for 12 months after surgery.

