6.3 Chemotherapy Guidelines

Chemotherapy will be given as per standard of care and should begin 2 to 4 weeks after completion of radiotherapy. Recommended total neoadjuvant chemotherapy regimens are:

- CAPOX (capecitabine/oxaliplatin)
- FOLFOX (oxaliplatin, leucovorin, and 5-FU)
- FLOT (docetaxel, oxaliplatin, leucovorin, and 5-FU)

However, the treating medical oncologist may prescribe other SOC total neoadjuvant chemotherapy regimen upon discussion with the WUSM PI. Additionally, if one regimen is not tolerated, subjects can move between regimens for a goal of 4 months of chemotherapy treatment total prior to surgery.

Patients who are unable to complete their total neoadjuvant therapy regimen may complete the chemotherapy postoperatively, at the discretion of the treating physician. Postoperative chemotherapy should start within 3 months of surgery. Patients who are medically inoperable will continue to receive chemotherapy until the entire regimen is complete.

A maximum (cumulative) delay of treatment of 4 weeks (or single delay of 3 weeks) is allowed per protocol due to factors/AEs listed in Section 7.0 (i.e., chemotherapy should be completed within a 5-month period). Cumulative delays in excess of 4 weeks, or single delays in excess of 3 weeks, will need to be discussed with the Principal Investigator in regard to proceeding to surgical resection. Such cases will need to be individualized depending on the clinical scenario. Please note that chemotherapy administration and AE assessment should be performed under the supervision of a medical oncologist. Dosing is to follow standard of care recommendations per institutional guidelines.

Interval imaging during chemotherapy, if obtained, is at the discretion of the treating physician.

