APPENDIX E: Study-Specific DSM Tables

Protocol Objectives and Subject Evaluability			
Objective	# of patients evaluable for this endpoint to date		
Primary			
To quantify the pCR rate in gastric cancer patients			
treated with preoperative radiation followed by total			
neoadjuvant chemotherapy.			
Secondary			
To quantify the proportion of patients able to complete a			
full course of total neoadjuvant chemotherapy			
To quantify the local control rate of gastric cancer			
patients treated with preoperative radiation followed by			
chemotherapy			
To quantify the toxicity of gastric cancer patients treated			
with preoperative radiation followed by chemotherapy			
To quantify the overall survival in gastric cancer patients			
treated with preoperative radiation followed by			
chemotherapy			
To quantify the disease-free survival in gastric cancer			
patients treated with preoperative radiation followed by			
chemotherapy			
Exploratory			
To quantify the deviation in dose to the tumor due to			
variation in stomach position			
To quantify the deviation in dose to the nearby OARs			
due to variation in OAR position			
To determine the distribution of TCGA molecular			
subtypes in gastric adenocarcinoma after radiation and			
chemotherapy			
To identify differentially expressed post-treatment			
biomarkers			
To correlate circulating tumor DNA (ctDNA) levels with			
clinical outcomes			

Interim Analysis and Early Stopping Rules				
Does the study design include an interim toxicity analysis?				
No				
Does the study design include an interim futility analysis?				
No				
Are there early stopping rules that outline circumstances under which the study must be				
suspended or closed?				
Yes				

If yes, please insert text describing early stopping rules from the protocol:

There will be a lead-in safety cohort of 5 patients, monitored for 30 days after completion of RT. If there is one treatment-related patient death, then the safety cohort will be expanded to 10 patients. If there are two or more treatment-related deaths, the radiation dose will be decreased to 20 Gy in 5 fractions. The trial will be terminated if there are more than three treatment-related deaths (equaling approximately 10% of the entire projected accrual).

If yes, please provide data describing whether the stopping rules have been met (by indicating whether there have been any treatment-related grade 5 toxicities in the safety lead-in cohort):

	Response				

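### The 30-day lead-in cannot cover chemotherapy deaths as Section 2.3.1 says it does, and Appendix E collects stopping-rule data only from the lead-in although the termination rule is scaled to the whole trial

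*Combined protocol and SAP*

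**What the plan says.** **Purpose.** Section 2.3.1 describes a lead-in of 5 to 10 patients "to ensure there are no grade 5 toxicities related to adaptive SCRT (or SOC chemotherapy after adaptive SCRT" (the closing bracket follows in the text). For the stopping rules, Section 6.1 likewise says that treatment-related "refers to both adaptive SCRT and SOC total neoadjuvant chemotherapy".

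**Window.** The only time limit in Section 6.1 is in its first sentence: "There will be a lead-in safety cohort of 5 patients, monitored for 30 days after completion of RT".

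**Actions (Section 6.1).**
- One treatment-related death expands the safety cohort to 10.
- Two or more reduce the radiation dose to 20 Gy in 5 fractions. No window or population is given.
- More than three end the trial. No window is given, but the count is explained as "equaling approximately 10% of the entire projected accrual".

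**Chemotherapy timing (Section 6.3).** Chemotherapy "should begin 2 to 4 weeks after completion of radiotherapy", "for a goal of 4 months of chemotherapy treatment total prior to surgery". With the permitted delays, "chemotherapy should be completed within a 5-month period". A patient who cannot finish before surgery may complete chemotherapy afterwards.

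**Reporting.** Appendix E reproduces the Section 6.1 rules, then asks for data on whether they have been met by indicating "whether there have been any treatment-related grade 5 toxicities in the safety lead-in cohort". It answers no to an interim toxicity analysis and yes to early stopping rules.

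**Dose.** Section 7.1 says that radiotherapy has no dose reductions. It does not mention the 20 Gy rule.

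**The concern.** Three pieces of text do not fit together.

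1. The lead-in is given a chemotherapy task, but its window closes when chemotherapy has barely begun. A lead-in with no deaths by day 30 would say little about fatal toxicity of chemotherapy given after this radiotherapy, which Section 2.3.1 says it checks.
2. The termination rule is scaled to the full accrual, but the form that tells the monitors whether the rules are met asks only about the lead-in. Completed as written, it would set deaths among 5 to 10 patients against a threshold meant for 36.
3. The 20 Gy sentence can be read as a lead-in rule, because it directly follows the expansion sentence, or as a trial-wide rule, because it does not name the cohort. These are very different rules.

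At stake is consistent application. In a multicentre trial, sites and monitors could reach different decisions from the same deaths.

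**Working it through.** **The plan's own figure.** Section 6.1 equates more than three deaths with about 10% of accrual, and accrual is 36 (Section 2.3.1).
- 10% × 36 = 3.6; 3/36 = 8.3%; 4/36 = 11.1%.

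Four deaths is the first count above 10%, so the figure reproduces with the whole trial as denominator. It would not with the lead-in: 4/10 = 40% and 4/5 = 80%.

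**Overlap of the window with chemotherapy.** Both clocks start at completion of radiotherapy. Overlap = 30 − start day.
- Earliest start, day 14: 30 − 14 = 16 days.
- Latest start, day 28: 30 − 28 = 2 days.
- Share of 4 months (121.75 days): 2/121.75 = 1.6% to 16/121.75 = 13.1%.
- Share of 5 months (152.2 days): 2/152.2 = 1.3% to 16/152.2 = 10.5%.

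To follow the whole course, a window would have to run about 14 + 122 = 136 days (earliest start, no delay) to 28 + 152 = 180 days (latest start, 5 months).

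**How far the readings differ.** The documents give no treatment-related death rate, so p, the full-course risk per patient, is an assumption shown over a range. Deaths are taken as independent and binomial.

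- 20 Gy rule, lead-in reading: P(X ≥ 2 of 5) + P(X = 1 of 5) × P(X ≥ 1 of the next 5). At p = 2%: 0.0038 + 0.0922 × 0.0961 = 0.0127. This is an upper bound, because the 30-day risk cannot exceed the full-course risk.
- 20 Gy rule, trial-wide: P(X ≥ 2 of 36) = 1 − (1 − p)^36 − 36p(1 − p)^35. At p = 2%: 1 − 0.4832 − 0.3550 = 0.162.
- Termination, trial-wide: P(X ≥ 4 of 36).

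| Assumed p | 20 Gy, lead-in (at most) | 20 Gy, 36 patients | Termination, 36 patients |
|---|---|---|---|
| 1% | 0.3% | 5.0% | 0.05% |
| 2% | 1.3% | 16.2% | 0.6% |
| 3% | 2.7% | 29.4% | 2.2% |
| 5% | 6.9% | 54.3% | 10.4% |

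The 36-patient columns assume that all 36 are treated and that a dose change leaves p unaltered. As proportions, two deaths are 2/5 = 40% or 2/10 = 20% of a lead-in, but 2/36 = 5.6% of the trial.

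**Termination judged on lead-in data, as Appendix E prompts.** Even at an assumed 10% risk, P(X ≥ 4) is 0.05% in 5 patients and 1.3% in 10, against 49.2% in 36. Assessed from the lead-in alone, the rule could hardly ever be met.

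**The case against.** **Section 6.1 already reads as trial-wide.** Its heading separates the cohort from the stopping rules, only the first two sentences name the cohort, and termination is scaled to total accrual. Counting the full chemotherapy course as treatment also makes little sense if the rules end at day 30. For termination this stands: the population is implied. A reader might infer that termination applies only to the lead-in, or has no population at all; the text does not support that. What remains is that the rule states no window and the Appendix E prompt contradicts it. For the 20 Gy rule the argument is weaker, because that sentence continues the expansion rule.

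**Later deaths are already seen.** This also stands. Adverse events are tracked to 12 months after surgery or definitive end of treatment (Section 8.0). Serious events reach the coordinating investigator within one working day or 24 hours (Sections 8.2 and 8.3). DSM reports include toxicity tables by site and participant-level survival (Section 12.0), and the Appendix E survival table records cause of death. A reader might infer that late chemotherapy deaths would go unnoticed; they would not, and the monitors may act on judgement. But no text ties these data to the Section 6.1 counts.

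**Day 30 suits the experimental component.** Fair: the radiotherapy is what is new, and chemotherapy is standard of care. That justifies the window, but not the wider purpose in Section 2.3.1. The 1.6% to 13.1% is calendar time; it should not be read as the share of fatal risk observed.

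**A trial-wide 20 Gy rule may be unwise.** Agreed. It would change the radiation dose in response to deaths that may be due mainly to standard chemotherapy, with a 16.2% to 29.4% trigger probability at an assumed 2% to 3% risk. The documents do not show which scope is right.

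**Conclusion.** The point holds as an inconsistency between the lead-in's stated purpose, the stopping rules and the reporting prompt. The lead-in window reaches 2 to 16 days of a 4- to 5-month chemotherapy course, so it cannot do the chemotherapy part of its task; this follows from the protocol's own timings and needs no assumption. The termination rule is implied to be trial-wide, but Appendix E asks for data on only 5 to 10 patients. The 20 Gy rule is undefined in both window and population, and its trigger probability differs more than sevenfold between readings at every assumed risk from 1% to 5%. Those probabilities rest on assumed death risks and independent deaths; they show that the readings differ, not that harm is likely.

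The primary endpoint, sample size and data collection are unaffected. The amendment should be made because it is cheap and removes a real conflict over when the trial must stop. Confidence is medium, since the intended scope of the 20 Gy rule cannot be settled from the documents.

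**What to change.** 1. **Section 6.1, termination.** State that the rule counts treatment-related deaths in all treated patients, from the start of radiotherapy through the end of protocol treatment, including any chemotherapy completed after surgery.
2. **Appendix E.** Replace the lead-in prompt with the cumulative trial-wide count of treatment-related deaths.
3. **Section 2.3.1.** Say that the 30-day lead-in addresses acute radiotherapy toxicity and early chemotherapy toxicity only, with later deaths covered by the trial-wide rule.
4. **20 Gy rule.** Have the team state whether it applies to the lead-in or to the whole trial, and show the trigger probability of the chosen version (at an assumed 2% risk, at most 1.3% or 16.2%). Cross-reference the rule in Section 7.1, which now rules out radiotherapy dose reductions.

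Day 30 can stay as the check that governs expansion from 5 to 10.

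**Cost.** A short amendment to four places, using data already collected, with no new visits and no accrual hold. The downside is that a trial-wide count may be triggered by deaths due mainly to standard chemotherapy. If the 20 Gy rule is made trial-wide, a late trigger changes the dose only for patients not yet irradiated.

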6.2 Radiation Therapy Guidelines

6.2.1 Dose, Fractionation, and Constraints

When feasible it is strongly recommended that radiotherapy begin on a Monday. It is accepted that occasional logistical delays may occur during radiotherapy treatment due to machine downtime or other issues. Radiotherapy as administered during this study may take up to 10 business days without being considered a protocol deviation.

Radiotherapy will consist of five fractions, delivered once daily, to a total dose of 25 Gy at 5 Gy per fraction. Radiation must be delivered with daily adaptive planning and MR gating or CBCT breath hold treatment. The stomach and OARs must be redrawn each day for the adaptive plan. Plans should be adapted to meet OAR constraints or improve coverage as needed for each day's unique anatomy.

Coverage: PTV V95% = 100%

Luminal GI structures: 30 Gy < 0.5 cc (hard constraint). 25 Gy < 0.5 cc (soft constraint). Kidneys V18 < 200cc. Spinal cord V28 < 0.03cc.

6.2.2 Treatment Planning Procedures

Image-based treatment planning and intensity modulated radiotherapy (IMRT) is permitted. Proton therapy is not permitted. Dose volume histogram (DVH) information for the target volumes, small bowel, and uninvolved colon (defined to be large bowel outside the clinical target volumes) is mandatory. This is to assist in interpreting outcome, including morbidity.

